4 LIST OF ABBREVIATIONS AND DEFINITION OF TERMS

ADR	Adverse drug reaction
AE	Adverse Event
AR	Adverse reaction
BDRM	Blind Data Review Meeting
CRF	Case Report Form
CRO	Contract Research Organization
CTM	Clinical trial manager
ENT	Ear-nose-throat
EudraCT	European Union Drug Regulating Authorities Clinical Trials
FAS	Full analysis set
FPI	First Patient In
GCP	Good Clinical Practice
GMP	Good Manufacturing Practice
ICD	International Classification of Diseases
ICH	International Committee of Harmonization
IEC	Independent Ethics Committee
IMP	Investigational Medicinal Product
Int.	International
LPO	Last Patient Out
MedDRA	Medical Dictionary for Regulatory Activities
NSAID	Non-steroidal inflammatory drugs
PPS	Per protocol set
SAE	Serious Adverse Event
SAP	Statistical analysis plan
SE	Societas Europaea
SUSAR	Suspected Unexpected Serious Adverse Reaction
V	Visit
VAS	Visual analogue scale

5 TRIAL SYNOPSIS

Trial code	ATi-2
Title of Trial	A Protocol of a Multicenter, Randomized, Open-Label, Comparative Study of Therapeutic Efficacy, Safety and Tolerability of Imupret application in the therapeutic concept of delayed prescription of antibiotics in children, aged 6-12 with severe acute tonsillitis.
Working title	Imupret in tonsillitis
Trial Design	open-label, exploratory, comparative, multicentre, randomized, prospective, parallel-group study.
Clinical phase	IV
Inclusion diagnosis	Acute tonsillitis
Trial objectives	
Assessment of the influence of Imupret (drops) prescriptions in the therapeutic concept of delayed prescription of antibiotics to:
 
 • need for antibiotics • regression of the tonsillitis symptoms • duration of antipyretics administration
Number of patients	approximately N=200 (1:1 ratio active treatment: reference)
Specialization of investigator	Head of Department of Otorhinolaryngology Head & Neck Surgery
Time schedule	Planned FPI (First patient in): approximately February 2019 Planned LPO (Last patient out): approximately December 2019
Efficacy endpoints	
The main criterion (main variable):
 
 - decrease in the severity of each symptom (complaint) that is part of the Mclsaac scale of tonsillitis manifestations, up to 1 point or less. This variable is dichotomous, with the categories "treatment effective" and "treatment not effective": - Treatment is effective - reducing the severity of each symptom (complaint) that is part of the Local Tonsillitis Manifestation Scale (0-15), of tonsillitis manifestations, up to 1 point or less in the evaluation stages. Absence of indications for prescribing antibacterial therapy - Treatment is not effective - the condition given for the category "therapy is effective" is not met.
Secondary end-points	
Secondary variables:
 
 - a decrease in the severity of the symptoms of the underlying disease, at the 2- nd, 3 -rd and 4- th visits compared to the 1- st visit. - decrease in the total score (the sum of scores for each symptom) according to the scale of local manifestations of tonsillitis at the 2-nd, 3-rd and 4-th visits in comparison with the 1-st visit. - a decrease in temperature in the armpit at the 2-nd and 3-rd visits compared to the 1-st visit. - a patient's self-assessment of the quality of life (every day). - Duration of NSAID administration. -Therapy compliance
Safety evaluation	
 - Adverse events (AEs), serious adverse events (SAEs) - Incidence of adverse drug reactions (ADRs)

	
- Overall assessment of tolerability
												

Methodology
	
 1. Medical history, demographic and anthropometric data at screening. 2. Complaints, patient questioning by organs and systems – at each visit, including any unscheduled visit and telephone contact. 
All complaints are assessed using a 4-point rating scale, beginning from the visit at which the complaint was identified for the first time.
 
 3. Physical examination: skin and visible mucosa examination, palpation of abdomen and lymph nodes, oropharyngoscopy are performed at each visit including any unscheduled visit. 
Symptoms are assessed using a 4-point rating scale, beginning from the visit at which the symptom was identified for the first time.
 
 4. Evaluation of probability of acute bacterial tonsillitis in accordance to McIsaac scale (sum of scores) 
  
 McIsaac scale (sum of scores)	The probability of the identification of β-hemolytic streptococcus in a smear from pharynx	
   
 -1 or 0	1%	
 
 1	10%	
 
 2	~17%	
 
 3	~35%	
 
 4 or 5	~50%	
  
 
 5. Complaints included in the Local Tonsillitis Manifestations Scale are assessed at each visit including any unscheduled visits 6. Symptoms included in the Local Tonsillitis Manifestations Scale are assessed at each visit 7. Axillary temperature assessment at each visit including any unscheduled visits. 8. Clinical blood count, urinalysis and blood chemistry according to the investigator's decision. 9. Self-assessment of the patient's state of health by him/herself and (or) his/her parents using a visual analogue scale is performed on a daily basis. 	McIsaac scale (sum of scores)	The probability of the identification of β -hemolytic streptococcus in a smear from pharynx	-1 or 0	1%	1	10%	2	~17%	3	~35%	4 or 5	~50%
McIsaac scale (sum of scores)	The probability of the identification of β -hemolytic streptococcus in a smear from pharynx												
-1 or 0	1%												
1	10%												
2	~17%												
3	~35%												
4 or 5	~50%												

Inclusion criteria
	
 1. Children (males/females), 6 - 12 years old, with severe acute tonsillitis. 2. Possibility to initiate therapy within 72 hours since the onset of the disease symptoms. 3. Score 4-5 according to Mclsaac Scale. 4. Patient's and (or) one of his/her parents' willingness and ability to fulfil the requirements of the Study Protocol. 5. Signed informed consent of the patient and (or) his/her parents for participation in the study.

Exclusion criteria
	
 1. Score -1 to 3 according to Mclsaac Scale. 2. Indication for hospitalization, including: 3. purulent complications (peritonsillar abscess and others); 4. severe general condition. 5. Indication for immediate initiation of systemic antibiotic therapy 6. patients at risk of developing severe complications, including e.g. clinically relevant concomitant diseases of heart, lungs, kidneys, liver, neuromuscular apparatus, cancer diseases, immunosuppression, diabetes mellitus, cystic fibrosis. 7. suspected infectious mononucleosis (by clinical signs); 8. use of systemic antibacterial or antifungal agents, systemic glucocorticosteroids, cytostatics, immunomodulatory drugs, "interferons" or interferon derivatives during the last 14 days prior to inclusion; 9. presence of haemorrhagic or pronounced necrotic process in oral cavity or pharynx, including the lymphoid ring. 10. Intolerability or individual hypersensitivity to any of the study drug ingredients and the reference treatment scheme.

Sample size calculation
	
Justification of the number of subjects
 
This trial is parallel, two-group, with the same size groups.
 
The planned test power is 80% (the probability of making a second kind error is 0.2), the two-way probability of making a type 1 error is 0.05. The sample size was estimated by the main variable of the clinical trial.
 
Thus, this trial was a comparative for superior efficiency.
 
When proving superior therapeutic efficacy, the following statistical hypotheses are tested:
 
H0: e £ d versus On: e > d, where d is the limit of greater efficiency — the marginal value of clinically important differences, at which it can be considered that the tested drug exceeds its effectiveness by control (in this study it was taken equal to 15%); e - estimated (observed) differences between groups in therapeutic efficacy.
 
Given that the main variable is dichotomous, the size of each group can be estimated using the following expressions:
 
n control = k · n main
 $n_{main} = \frac{(z_{\alpha} + z_{\beta})^2}{(\varepsilon - \delta)^2} \cdot \left[\frac{p_{control} \cdot (1 - p_{control})}{k} + p_{main} \cdot (1 - p_{main}) \right]$ 
where: z_{α} and z_{β} —the corresponding percentage points of the standard normal distribution; d - the minimum acceptable value of clinically important differences; e - presumed (observable) differences between groups on therapeutic efficacy (the difference between the shares of positive results in groups); pcontrol and p main —shares of positive results in the

main and control groups, respectively; k - coefficient for unequal number of patients in groups (control is greater than the main); n_{main} и $n_{control}$ - the planned number of patients in the main and control groups, respectively; α is the boundary value of the error of the 1st kind (level of significance); β - is the boundary value of the error of the second kind.

In the planned study, it was assumed that the number of patients in the main and control groups was the same ($k = 1$), the significance level was $\alpha = 0.05$ (two-sided); the boundary value of the error of the second kind is $\beta = 0.2$ (which makes it possible to achieve a research power of 80%). Baseline data and the results of calculations using the above formula are given in Table. 1.

Table 1 - Baseline and Sample Size Estimation Results

Statistical indicator	Value of the indicator
Multiplicity factor k	1
Boundary probability error of the first kind α	0,025
The probability of an error of the second kind β	0,2
The percentage point S.N.R. for α	1,96
The percentage point S.N.R. for β	0,84
The observed frequency of the positive effect for the control group $p_{control}$	0,75
Estimated value of the positive effect for the main group p_{main}	0,90
The value of the clinically important differences d	0,15
Estimated differences between groups e	0,0
The size of the main group n_{main}	97
The size of the control group $n_{control}$	97
Estimated share of departures	3
Adjusted main group size	100
Adjusted control group size	100

The final number of patients in each group was adjusted for their possible dropout. Thus, the final number of subjects in each group was 100 patients (200 patients in total).

Test treatment	
 - Treatment with Imupret® oral drops according to the respective Summary of Product characteristics (Imupret® coated tablets or oral drops during acute period for 5 days, afterwards switch to the subacute dosage regimen for further 28 days) - Sparing diet; fractional feeding (5-6 times a day) in small portions with the exception of coarse, spicy, heavily digestible foods - Elimination of factors irritating pharyngeal mucosa (thermal, chemical) 
 - As needed, Paracetamol (Acetaminifen) in a single dose of up to 400 mg not more than 3 times daily or paracetamol in a single dose of up to 500 mg 3-4 times daily (if necessary). - Topical agents such as Benzydamine, Lidocaine as needed (in case of severe sore throat). 	
Reference treatment	
 - Sparing diet; fractional feeding (5-6 times a day) in small portions with the exception of coarse, spicy, heavily digestible foods - Elimination of factors irritating pharyngeal mucosa (thermal, chemical) - As needed, Paracetamol (Acetaminifen) in a single dose of up to 400 mg not more than 3 times daily or paracetamol in a single dose of up to 500 mg 3-4 times daily (if necessary). - Topical agents such as Benzydamine, Lidocaine as needed (in case of severe sore throat). 	
Investigational Medicinal Product	Active (add on) treatment	Imupret® oral drops
	Mode of administration and dosage regimen	
Imupret® oral drops
 
Dosage for acute symptoms:
 
Children from 6 to 12 years: 15 drops 5-6 times daily
 
Adults and adolescents from the age of 12 years: 25 drops 5-6 times daily
 
Dosage after acute symptoms have subsided:
 
Children from 6 to 12 years: 15 drops 3 times daily
 
Adults and adolescents from the age of 12 years: 25 drops 3 times daily

Duration of treatment	
Disease will be evaluated 36-48 hours prior to active treatment.
 
Active Imupret® treatment group: 10 treatment days
 
Reference treatment group: 10 days
 
Afterwards, there will be a follow up observation phase of 1 months
	

SCHEDULE OF ASSESSMENTS

V1		V2		V3 (Telephone call)					V4	V5
day 1	day 2	day 3	day 4	day 5	day 6	day 7	day 8	day 9	day 10	day 28

Study group 1

Imupret (dosage acute phase)
Reference treatment

Study group 2

Reference treatment

V1	day 1	Screening, randomization, prescription of treatment
V2	day 3	Status evaluation, possible prescription of antibiotics
V3	day 5 ±1	Evaluation of treatment efficacy, telephone call
V4	day 10 ±1	Evaluation of treatment efficacy, end of reference treatment
V5	day 28	Telephone call

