8.5 Time schedule and visits

Four scheduled visits will be performed during the first phase of the study:

First study phase

- 1 visit (1st day): screening, randomization and treatment; evaluation by Mc Isaac Score scale; LTM Scale (Local Tonsillitis Manifestation Scale): (5 symptoms: Sore throat at swallowing (0 – absent, 1 – mild, 2 – moderate, 3 – severe / pronounced); Sore throat at rest; Throat irritation at rest; Palatine tonsils hyperemia; Palatine tonsils edema); Patients self-assessment (VAS; 0-10)

- 2 visit (3rd±1 day): intermediate evaluation of the effectiveness of treatment - clarification of the patient's condition, the need to prescribe an antibiotic; evaluation by LTM Scale, patients self-assessment (VAS; 0-10)
- 3 visit: intermediate evaluation of the effectiveness of treatment (day 5-day ±1) via telephone (or visit if necessary); patients self-assessment (VAS; 0-10)
- 4 visit: final (10th day ±1 day). Evaluation by LTM Scale (0-15), patients self-assessment (VAS; 0-10)
- 5 Follow up; day 28: evaluation of the long-term effects of treatment
- - An unscheduled visit can be made if the patient's condition worsens (according to the patient and / or the researcher, including if the symptoms of the disease persist or worsen, including but not limited to an increase in the temperature in the armpit above 38.0 ° C at the 3rd and / or subsequent days of treatment).
- The total duration of the treatment: 10 days
- The total duration of the study for one patient is not longer than 38 days.

Any unscheduled visit may be carried out in case of worsening of the patient's condition (at patient's and/or investigator's opinion), including persistence or aggravation of the disease symptoms.

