10.6 Clinical assessments and parameters

Assessment of tonsillitis will be performed according to the Local Tonsillitis Manifestation Scale. In detail the following symptoms will be investigated:

Local Tonsillitis Manifestation Scale

- Sore throat at swallowing (0 – absent, 1 – mild, 2 – moderate, 3 – severe / pronounced);
- Sore throat at rest, i.e. during the intervals between swallowing acts (0 – absent, 1 – mild, 2 – moderate, 3 – severe / pronounced);
- Throat irritation at rest, i.e. during the intervals between swallowing acts (0 – absent, 1 – mild, 2 – moderate, 3 – severe / pronounced);
- Cough associated with throat discomfort (0 – absent, 1 – mild, 2 – moderate, 3 – severe / troublesome).
- Posterior pharyngeal wall hyperaemia (0 – absent, 1 – mild, 2 – moderate, 3 – severe / pronounced);
- Palatine tonsils hyperaemia (0 – absent, 1 – mild, 2 – moderate, 3 – severe / pronounced);
- Palatine tonsils oedema (0 – absent, 1 – mild, 2 – moderate, 3 – severe / pronounced).

Diagnoses will be further refined using the Mclsaac Scale

Symptom	Score
Body temperature exceeding 38°C	+1
Absence of cough	+1
Painful anterior cervical lymph nodes	+1
Tonsillar oedema and/or exudate on tonsils	+1
Age 3–14 years old	+1
15–44 years old	0
>45 years old	- 1

Assessment of type of tonsillitis:

Score 0 – probability of group A β -haemolytic streptococcus (GABHS) infection is 1-2%;

Score 1 – probability of GABHS infection is 5-10%;

Score 2 – probability of GABHS infection is 11-17%;

Score 3 – probability of GABHS infection is 28-35%;

Score 4 – probability of GABHS infection is 51-53%;

Self-assessment of the quality of life by the patient.

- Sore throat at swallowing (0 –10 points VAS);
- Sore throat at rest, i.e. during the intervals between swallowing acts (0 –10 points VAS);
- Throat irritation at rest, i.e. during the intervals between swallowing acts (0 –10 points VAS);
- Cough associated with throat discomfort (0 –10 points VAS).

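### The main variable is not defined consistently (scale, item list, visit, place of antibiotic need), and the 75% and 90% behind 97 per arm are tied to no version or visit

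*Protocol*

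**What the plan says.** **Scale.** The Efficacy endpoints cell of the synopsis introduces the main variable as a "decrease in the severity of each symptom (complaint) that is part of the" McIsaac scale, down to 1 point or less. The same cell then defines effective treatment as reducing "each symptom (complaint) that is part of the Local Tonsillitis Manifestation Scale (0-15), of tonsillitis manifestations, up to 1 point or less". Section 12.2.2 and the Primary endpoint section of the SAP use LTM scores qualified in some unexplained way by McIsaac. They dichotomise these scores without giving a cut-off.

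**Items.** Section 8.5 describes the LTM scale as "5 symptoms: Sore throat at swallowing" and four others. Section 10.6 lists seven items under the same name, adding cough and "Posterior pharyngeal wall hyperaemia".

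**Visit and antibiotics.** The synopsis rule reads "up to 1 point or less in the evaluation stages. Absence of indications for prescribing antibacterial therapy". Section 12.2.2 and the SAP evaluate the scores at every visit. They list need for antibacterial therapy as a second, separate main criterion, and section 7 puts that need first among the aims. Sections 8.3.3 and 10.2 say that children given antibiotics get a separate evaluation, without saying what that means for the main comparison.

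**When the LTM scale is scored.** Section 8.5 lists it at visits 1, 2 and 4 and labels visit 4 as final. The synopsis Methodology says the scale's complaints "are assessed at each visit including any unscheduled visits". A secondary variable uses the "scale of local manifestations of tonsillitis at the 2-nd, 3-rd and 4-th visits", although visit 3 is a telephone call unless a visit is needed.

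**Specification and sample size.** Section 12.2 and the SAP leave the biometrical specifications until the database has been closed. The synopsis bases the sample size on the main variable, with 0.75 for control and 0.90 for the main group.

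**The concern.** A responder variable needs a scale, an item list, a cut-off, a time point and a rule for children who need antibiotics. Only the synopsis gives a cut-off, and it applies it to two scales. No document fixes the visit, and the item list and the antibiotic rule differ between sections. The SAP, which should settle such questions, repeats section 12.2.2 almost word for word and adds nothing.

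Two competent analysts could therefore report different main results from the same 200 children without either departing from the plan. The trial is open-label, so outcomes by arm can be known when the version is chosen, and a reader could not tell whether the choice followed the data. The sample size has the same gap: its two rates belong to a variable whose version and visit are not stated.

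**Working it through.** **1. Scale.** In the McIsaac table of section 10.6, fever, absence of cough, painful nodes, "Tonsillar oedema and/or exudate on tonsils" and age each score +1 at most. A threshold of 1 or less is therefore met on every item by every child at entry, and the rule cannot separate responders from non-responders. LTM items run from 0 to 3, so there the same threshold can be failed.

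**2. Items.** Five items give a maximum of 5 × 3 = 15; seven give 7 × 3 = 21. The 0-15 range in the synopsis and section 8.5 fits the five-item list only. Each item must reach 1 or less, so every seven-item responder is also a five-item responder, and the seven-item rate cannot exceed the five-item rate.

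The gap may be small for cough. At ages 6-12 the age point is certain, so a McIsaac score of 4-5 needs three or four of the other four points: 4 + 1 = 5 patterns. Cough at entry loses the absence-of-cough point, so the other three must all be present: 1 pattern of 5. This counts patterns, not children; the documents give no frequencies.

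**3. Visit.**

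| Visit | LTM in 8.5 | LTM in synopsis | Contact |
|---|---|---|---|
| V2, day 3 | yes | yes | in person |
| V3, day 5 ± 1 | no | yes | telephone, or visit if needed |
| V4, day 10 ± 1 | yes | yes | in person |

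Tonsillar redness and swelling have to be examined, so the practical choice for the main variable is V2 or V4. The endpoint wording does not decide between them.

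**4. Antibiotics.** Under the synopsis rule, a child with an indication is not effective. Under section 12.2.2 and the SAP, need is counted by itself, and nothing says that it also makes the child a non-responder. The full analysis set in section 12.2.1 has no antibiotic exclusion, and antibiotics are not among the groups in section 8.3.4 that require withdrawal. The last sentence of 8.3.4 does allow withdrawal, at the investigator's discretion, after any medication that might interfere with the objectives.

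**5. Sample size.** Inputs from the synopsis and its Table 1: z = 1.96 and 0.84, control 0.75, main group 0.90, k = 1, and 0.15 squared in the denominator. (Table 1 lists e = 0.0 and d = 0.15. I read the 0.15 as the difference 0.90 − 0.75, which gives the same square; what this means for the stated hypothesis is a separate question.)

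n = (1.96 + 0.84)² / 0.15² × [pc(1 − pc) + pm(1 − pm)] = 348.44 × [0.1875 + 0.0900] = 348.44 × 0.2775 = 96.69, rounded up to 97. The plan's figure reproduces.

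The following is an illustration on assumed rates, keeping the 15-point difference. Power is for 100 per arm, two-sided 5%, by the pooled-variance normal formula.

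| Control / main | Variance sum | n per arm | Power at 100 per arm |
|---|---|---|---|
| 80% / 95% | 0.2075 | 72.3 → 73 | 90% |
| 75% / 90% (plan) | 0.2775 | 96.7 → 97 | 80% |
| 70% / 85% | 0.3375 | 117.6 → 118 | 72% |
| 60% / 75% | 0.4275 | 148.96 → 149 | 62% |

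(Unrounded z values give 150 in the last row.)

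**The case against.** The best defence is that a sensible reading exists. The McIsaac sentence looks like a drafting slip, put right by the LTM definition in the same cell. Five items match the 0-15 range, and visit 4 is called final. Sections 8.1, 8.2 and 12.2 call the trial exploratory, and section 12.2 promises technical details before analysis. Much of this stands: five items at visit 4 is the best-supported reading, and the exploratory label lowers the stakes. It does not settle the matter. Section 12.2.2 and the SAP do not repeat that reading, 10.6 contradicts its item list, and the synopsis still sizes the trial for superiority on this variable. The promise of details before analysis stands beside the clause that waits for database closure, and neither prevents a choice made after outcomes by arm are visible.

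A reader might infer three stronger things that the documents do not support:

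- **That children given antibiotics drop out of the main comparison.** No passage requires this, and the synopsis rule counts an indication as not effective. What exists is an ambiguous phrase and a discretionary withdrawal clause.
- **That 97 is miscalculated, or points to only one pair of rates.** It reproduces, and 10%/25% has the same variance sum (0.09 + 0.1875 = 0.2775) and also gives 97. What cannot be traced is the origin of the rates.
- **That the seven-item list would lower response or power by a known amount.** Only the direction of the response rate is fixed (equal or lower). The documents give no item-level data, so any power figure would be invented.

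**Conclusion.** The point holds and must be fixed before analysis. The main variable differs between sections in scale, item list and the role of antibiotic need, and no section names its visit. In an open-label trial with specifications left until database closure, the main result could depend on a choice made late. The size and direction of any effect on the result are unknown; nothing here shows that the result will favour either arm.

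The sample size is arithmetically sound for 75% against 90%, but those rates are tied to no definition, visit or source. The range of 73 to 149 per arm rests on assumed control rates of 80% down to 60% with the 15-point difference held constant. It shows how much n depends on the definition behind the rates; it does not estimate an error.

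**What to change.** Use one definition, in identical words, in the synopsis, section 12.2.2 and the SAP. Suggested text: *Effective = each LTM item scored 1 or less at [one named visit], with no indication for antibiotics up to that visit; otherwise not effective.* Then:

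- Have the sponsor confirm both the item list and the visit. The five items of section 8.5 (0-15) at visit 4 (day 10 ± 1) are the best supported. Make section 10.6 agree.
- Take McIsaac out of the responder rule and keep it for eligibility and diagnosis.
- State that children with an antibiotic indication or prescription stay in the main comparison as not effective, including any withdrawn at the investigator's discretion. State that the separate evaluation in 8.3.3 and 10.2 is an added description.
- State the status of antibiotic need by arm: co-primary or key secondary.
- Say which definition and visit the 75% and 90% describe, and their source, or label them as assumptions. If they belong to another version, recompute n and restate the power at 100 per arm.
- Replace the database-closure clause in section 12.2 and the SAP with a dated specification fixed before any comparison of outcomes by arm.

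The cost is wording only, with no new data. Items and visits outside the definition become descriptive, and the restated power may fall below 80%. Antibiotic indications after visit 2 would have to be picked up from the visit 3 contact, unscheduled visits, recorded prescriptions or intake, and the visit 4 medication check.

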Checks for general well-being (AE-checks), checks of restrictions and medication will be performed.

The investigator will estimate indicators for prescription of antibiotics and will decide whether a patient will remain on the study treatment or not. If an antibiotic agent is prescribed, details will be documented and the patient will be instructed about the mode of administration. Intake of

antibiotic drug will be documented in the CRF. Patients with intake of antibiotics will be evaluated separately. At the discretion of the investigator the patient may be advised not to take IMP anymore. If so, this will be documented as well.

Self-assessment of the patient's throat pain by him/herself and (or) his/her parent(s) using a visual analogue scale (VAS) is performed afterwards. Moreover, forms for VAS assessment will be handed over to the patient. The patient will have to assess his/her sore throat every study day until visit 4 on study day 10±1.

10.3 Interim evaluation of treatment efficacy- Visit 3

Visit 3 (V3) will be performed on day 5 ±1 by a telephone call.

Intermediate evaluation of the effectiveness of treatment (day 5-day ±1) via telephone (or visit if necessary); patients self-assessment (VAS; 0-10)

10.4 Treatment efficacy, end of Reference treatment - Visit 4

At visit 4 (V4) on day 10 ±1 the status of the disease will be again evaluated.

A physical examination of vital signs (blood pressure, pulse rate, body temperature (axillar)) will be performed. All physical examinations done at V1 including skin and visible mucosa, palpation of abdomen and lymph nodes, oropharyngoscopy will be repeated to assess the status of the tonsillitis.

Again, objective symptoms included in the "Local Tonsillitis Manifestation Scale".

Checks for general well-being (AE-checks), checks of restrictions and medication will be performed.

Self-assessment of the patient's throat pain by him/herself and (or) his/her parent(s) using a visual analogue scale (VAS; 0-10 points) is performed. Forms of VAS assessment will be collected from the patient.

10.5 Treatment efficacy, end of treatment - Visit 5

Visit 5 (V5) will be performed on day 28 by a telephone call (for both the groups).

Checks for general well-being (AE-checks), checks of restrictions and medication will be performed.

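### Three secondary variables are defined at Visit 3, by default a telephone call at which the LTM total, the examined LTM items and a clinic temperature cannot be obtained; the sections on this must be reconciled

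*Protocol*

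**What the plan says.** **Endpoint visits.** The synopsis lists three secondary variables that include Visit 3:

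- "a decrease in the severity of the symptoms of the underlying disease", at Visits 2, 3 and 4 against Visit 1;
- the fall in the total score "according to the scale of local manifestations of tonsillitis at the 2-nd, 3-rd and 4-th visits in comparison with the 1-st visit";
- for body temperature, a shorter list of visits: "a decrease in temperature in the armpit at the 2-nd and 3-rd visits compared to the 1-st visit".

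**What Visit 3 is.** The synopsis schedule describes day 5 as "Evaluation of treatment efficacy, telephone call". Section 10.3 says "Visit 3 (V3) will be performed on day 5 ±1 by a telephone call". Section 8.5 describes it as "via telephone (or visit if necessary); patients self-assessment (VAS; 0-10". The VAS is the only instrument these two sections name for Visit 3. For Visit 2, by contrast, section 8.5 lists "the need to prescribe an antibiotic; evaluation by LTM Scale, patients self-assessment (VAS; 0-10", and for Visit 4 it again lists the LTM Scale. Sections 10.1, 10.2 and 10.4 place axillary temperature at Visits 1, 2 and 4.

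**What the synopsis methodology says.** It requires "Axillary temperature assessment at each visit including any unscheduled visits". It also places oropharyngoscopy and the LTM complaints and symptoms at each visit, and it has complaints taken at telephone contacts and scored on a four-point scale.

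**What the analysis text says.** Section 12.2.2 and the SAP evaluate the dichotomised main criterion per visit. Section 12.2.3 and the SAP list each LTM symptom score per visit, and axillary temperature at each measurement time point.

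**The concern.** An endpoint should be tied to visits at which its components are measured. Here the endpoint list, the visit descriptions, the synopsis methodology and the analysis list give different answers about day 5. Tonsil hyperaemia and oedema, and posterior pharyngeal wall hyperaemia in the longer list, are findings of a throat examination and cannot be obtained by telephone.

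An analyst following the synopsis literally would find the Visit 3 total and temperature either empty or available only for children brought in. Because the trial is open-label, the decision to bring a child in could differ by arm. There is no later safeguard. Section 12.2 and the SAP leave the analysis specification until after the database is closed and allow data-driven inference, so the handling of Visit 3 would be chosen with unblinded data in hand. What is at stake is the day-5 part of the symptom-regression objective, and any day-5 reading of the main criterion.

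**Working it through.** The plan states no figure on this point. The check sets the sections side by side and counts scale items.

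**Step 1. Visits named against visits measured.**

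| Visit | Default mode | LTM Scale named in section 8.5 | Axillary temperature named in sections 10.1–10.5 | Synopsis secondary variables |
|---|---|---|---|---|
| V1, day 1 | in person | yes | yes | baseline |
| V2, day 3 | in person | yes | yes | severity, LTM total, temperature |
| V3, day 5 | telephone | no | no | severity, LTM total, temperature |
| V4, day 10 | in person | yes | yes | severity, LTM total |

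- LTM total: the synopsis names V2, V3 and V4; it is measured after baseline at V2 and V4. In common: V2 and V4.
- Temperature: the synopsis names V2 and V3; it is measured after baseline at V2 and V4. In common: V2 only.

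**Step 2. How much of the LTM score a call can give.** Each item is scored 0 to 3.

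- Five-item list (section 8.5, range 0–15): three complaints, 3 × 3 = 9; two examined items, 2 × 3 = 6; total 15. By telephone at most 9 of 15.
- Seven-item list (section 10.6): four complaints, 4 × 3 = 12; three examined items, 3 × 3 = 9; total 21. By telephone at most 12 of 21.

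On neither list can the total be formed.

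**Step 3. The dichotomised criterion.** The synopsis calls treatment effective only if every LTM symptom falls to 1 or less and antibacterial therapy is not indicated. A call can show that a complaint is still above 1, and so that treatment is not effective. It cannot show that the examined items have reached 1 or less, so it can never establish that treatment is effective. A per-visit evaluation at a telephone Visit 3 is therefore one-sided at best.

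**Step 4. Which children could have full Visit 3 data.** Only those seen in person when necessary. Section 8.5 also gives worsening, persisting symptoms and an armpit temperature above 38.0 °C from day 3 as grounds for an unscheduled visit. Day-5 clinic readings would thus plausibly come from sicker or febrile children, selected in part on the outcome itself.

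**Step 5. Hypothetical illustration.** Suppose a child scores 2 on all five items at V1 and is unchanged on day 5. The V1 total is 5 × 2 = 10. A telephone sum of the three complaints is 3 × 2 = 6. If that sum were set against the full V1 total, the apparent fall would be (10 − 6)/10 = 40% with no change in the child. No section prescribes this calculation; it only shows why a partial sum must not be compared with a full one.

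**The case against.** The strongest reply is that the gap is narrow and partly covered elsewhere. Most of that is right.

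- *Symptom regression between days 3 and 10 is not lost.* A reader might infer that day 5 is the only observation in that interval. It is not: section 10.2 has the patient rate sore throat every study day until Visit 4. The four VAS items in section 10.6 match the four LTM complaints in the seven-item list. Day 5 is the only planned visit in the interval, not the only data point.
- *The Visit 4 temperature is not discarded.* A reader of the synopsis alone might infer that it goes unused. Section 12.2.3 and the SAP take temperature at every measurement time point, which includes Visit 4. The omission is in one synopsis bullet.
- *More than the VAS may be recorded.* The synopsis methodology has complaints scored at telephone contacts, and Visit 3 may be held in person. To say that nothing else can exist at Visit 3 goes too far.
- *Home temperature is unspecified, not ruled out.* The fever ground for an unscheduled visit is compatible with readings at home, and the case report form is not among the documents. What can be said is that no section asks for such a reading.
- *The 40% fall is not a forecast.* Section 12.2.3 and the SAP list individual symptom scores rather than a total, and scoring unobserved items as zero would affect both arms, so it would not by itself create a treatment difference.
- *The trial is declared exploratory.* True, but an exploratory variable still needs a visit at which it is measured.

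None of this supplies the examined items, the total or a clinic temperature for a child reached only by telephone. The wording that places everything at each visit deepens the contradiction, because a call cannot include oropharyngoscopy.

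**Conclusion.** The inconsistency is real and should be corrected. Three synopsis secondary variables (symptom severity, LTM total, armpit temperature) are set at a visit that by default is a telephone call. There at most 9 of 15 or 12 of 21 LTM points can be scored, no temperature reading is specified, and the dichotomised criterion cannot be fully assessed. For temperature, the synopsis and the visit descriptions share only one post-baseline visit, Visit 2.

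The conclusion assumes that Visit 3 takes place by telephone for most children, which is the stated default, and that hyperaemia and oedema are scored by examination, as section 10.1 describes. That children seen in person would be sicker, and that the choice might differ by arm, are plausible inferences rather than documented facts.

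The effect is confined to one time point. Visits 2 and 4, the daily VAS and the Visit 4 temperature in the analysis text are unaffected.

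**What to change.** Reconcile the synopsis endpoints, the synopsis methodology, sections 12.2.2 and 12.2.3 and the SAP, before any data are analysed, as follows:

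1. Analyse the LTM total, the examined LTM items, the dichotomised criterion and axillary temperature at Visits 2 and 4, each against Visit 1. This adds Visit 4 to the synopsis temperature variable and removes Visit 3.
2. At Visit 3, analyse the VAS, or a separately named patient-reported subscore compared with the same items at Visit 1.
3. List in-person Visit 3 and unscheduled findings separately, and do not pool them into Visit 3 efficacy summaries.
4. In the synopsis methodology, state which assessments apply to in-person visits only and which to telephone contacts.

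The cost is wording in the protocol and SAP. What is given up is a nominal day-5 comparison of LTM total and temperature that the telephone visit cannot deliver. If a day-5 temperature is wanted, a parent-read value would have to be specified, which is one more line on the daily VAS form.
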